#### **7.8.2.4. Emergency Situations**

In emergency situations, it may be necessary for study participants to change their dose of OAM and/or be treated with a non-study insulin. This will be allowed for up to 2 weeks total prior to Visit 21 (Week 32). If multiple situations last longer than 2 weeks total prior to Visit 21 (Week 32), a decision to keep the study participant in the study should be made only after consultation between the investigator and the Lilly CRP. The decision should be documented by a note to the investigator's file.

## 8. Discontinuation Criteria

### 8.1. Discontinuation from Study Treatment

#### 8.1.1. *Permanent Discontinuation from Study Treatment*

Possible reasons leading to permanent discontinuation of IP:

- **Subject Decision**
  - the study participant or the study participant's designee, for example, parents or legal guardian requests to discontinue IP.
- **Discontinuation due to a hepatic event or liver test abnormality.**
  - Study participants who are discontinued from IP due to a hepatic event or liver test abnormality should have additional hepatic safety data collected via eCRF.

Discontinuation of the IP for abnormal liver tests **should be** considered by the investigator when a study participant meets one of the following conditions after consultation with the Lilly designated medical monitor:

- ALT or AST >8X ULN
- ALT or AST >5X ULN for more than 2 weeks
- ALT or AST >3X ULN and total bilirubin level (TBL) >2X ULN or international normalized ratio >1.5
- ALT or AST >3X ULN with the appearance of fatigue, nausea, vomiting, right upper-quadrant pain or tenderness, fever, rash, and/or eosinophilia (>5%)
- alkaline phosphatase (ALP) >3X ULN
- ALP >2.5X ULN and TBL >2X ULN
- ALP >2.5X ULN with the appearance of fatigue, nausea, vomiting, right quadrant pain or tenderness, fever, rash, and/or eosinophilia (>5%)

In addition, study participants will be discontinued from the IP in the following circumstances:

- if a study participant is inadvertently enrolled and it is determined that continued treatment with IP would not be medically appropriate (see Section 8.1.3)
- if a study participant is diagnosed with an active or untreated malignancy (other than basal or squamous cell skin cancer, in situ carcinomas of the cervix, or in situ prostate cancer) after randomization
- if a study participant is diagnosed by the investigator with acute or chronic pancreatitis
- if a study participant is diagnosed with C-cell hyperplasia or medullary thyroid carcinoma after randomization

- if the investigator or sponsor decides that the study participant should be withdrawn from IP; if the investigator decides to permanently discontinue IP because of an SAE or a clinically significant laboratory value, Lilly or its designee should be alerted immediately.

Study participants discontinuing from the IP study treatment prematurely for any reason should complete AE and other follow-up procedures per Section 2 (Schedule of Activities), Section 9.2 (Adverse Events), and Section 9.4 (Safety) of this protocol.

Study participants who stop the IP permanently may receive another glucose-lowering intervention, if appropriate, and will continue participating in the trial according to the protocol to collect all planned efficacy and safety measurements.

### **8.1.2. Temporary Discontinuation from Study Treatment**

In certain situations after randomization, the investigator may need to temporarily discontinue (interrupt) IP (for example, due to an AE or a clinically significant laboratory value). If IP interruption is due to an AE, the event is to be documented and followed according to the procedures in Section 9.2 of this protocol. Investigators should inform the Sponsor that IP has been temporarily interrupted. Every effort should be made by the investigator to maintain study participants on IP and to restart IP after any temporary interruption, as soon as it is safe to do so. The data related to temporary interruption of IP will be documented in source documents and entered in the eCRF.

### **8.1.3. Discontinuation of Inadvertently Enrolled Study Participants**

If the sponsor or investigator identify a study participant who did not meet enrollment criteria and was inadvertently enrolled, then the study participant should be discontinued from study treatment unless there are extenuating circumstances that make it medically necessary for the study participant to continue on study treatment. If the investigator and the sponsor CRP agree that it is medically appropriate to continue, the investigator must obtain documented approval from the sponsor CRP to allow the inadvertently enrolled study participant to continue in the study with or without treatment with IP. Safety follow up is as outlined in Section 2 (Schedule of Activities), Section 9.2 (Adverse Events), and Section 9.4 (Safety) of the protocol.

## **8.2. Discontinuation from the Study**

Study participants will be discontinued in the following circumstances:

- if a study participant is diagnosed with any type of diabetes mellitus other than T2DM
- if a female study participant becomes pregnant, enrollment in any other clinical study involving an IP or enrollment in any other type of medical research judged not to be scientifically or medically compatible with this study

- participation in the study needs to be stopped for medical, safety, regulatory, or other reasons consistent with applicable laws, regulations, and good clinical practice (GCP)
- investigator decision
  - the investigator decides that the study participant should be discontinued from the study
  - if the study participant, for any reason, requires treatment with another therapeutic agent that has been demonstrated to be effective for treatment of the study indication, discontinuation from the study occurs prior to introduction of the new agent
- study participant decision
  - the study participant/study participant's designee, for example, parents or legal guardian requests to be withdrawn from the study

Study participants discontinuing from the study prematurely for any reason should complete AE and other safety follow-up per Section 2 (Schedule of Activities), Section 9.2 (Adverse Events), and Section 9.4 (Safety) of this protocol.

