### **General considerations**

Study procedures will be performed as listed in the Schedule of Activities (Section [2](#)).

In order to allow timely sampling for PK assessments, visits for collection of the samples will be scheduled within the required time windows provided in the Schedule of Activities (Section [2](#)).

Study participants will continue to use concomitant OAMs throughout the treatment period: discontinuation or changes to dose are not permitted, except in situations where dose adjustment or complete discontinuation is required per country-specific label or when allowed per study protocol (for further details see Section [7.7.2](#)).

Study participants will be instructed to document fasting plasma glucose (FPG) each day by using the values displayed on their CGM device after waking or using a finger-stick glucose measurement. In addition, two 6-point SMPG profiles (prior to and 2 hours after the morning, midday, and evening meals) should be documented on non-consecutive days in the week prior to the required visits noted in the Schedule of Activities using CGM-based glucose values, (Section [2](#)).

Study participants who develop severe, persistent hyperglycemia based on prespecified thresholds (see Section [7.8.2.3](#)) will receive a new glucose-lowering intervention (or rescue therapy) based on clinical judgment of the investigator (see [Table BDCM.4](#)). Study participants who need rescue therapy will continue on IP in the trial until they complete all study visits.

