### **Study Period 3: End-of-Treatment and Safety Follow-Up, Visits 21, 801, 802, and 803**

All randomized study participants should have a comprehensive efficacy and safety evaluation approximately 1 week after the last dose of IP and a safety follow-up visit approximately 6 weeks after the last dose of IP. During the safety follow-up study period, study participants will continue CGM and may be treated with an appropriate glucose-lowering regimen (see [Table BDCM.4](#)) if necessary. Study participants will also be required to return any remaining study diaries and used or unused IP to the investigative site.

Study participants who *complete the treatment period* will have a comprehensive End-of-Treatment efficacy and safety assessment (Week 32; Visit 21) approximately 1 week

after the last dose of IP and a safety follow-up assessment (Visit 801) approximately 6 weeks after the last dose of IP and 5 weeks after their End-of-Treatment assessment (Visit 801). During the safety follow-up study period, study participants will continue CGM, and may be treated with an appropriate glucose-lowering regimen (see [Table BDCM.4](#)) if necessary. Study participants will also be required to return any remaining study diaries and used or unused IP to the investigative site.

Study participants who *discontinue IP prior to completion* of the study for any reason should also have a comprehensive End-of-Treatment efficacy and safety assessment (Visit 802) approximately 1 week after the last dose of IP or as soon as reasonably possible thereafter, and should have a safety follow-up assessment (Visit 803) approximately 6 weeks after the last dose of IP. Study activities at Visits 802 and 803 are identical to Week 32 (Visit 21) and Visit 801, respectively.

Study participants who discontinue IP prior to study completion will be encouraged to remain in the study and to complete any scheduled study procedures that occur after their safety follow-up (Visit 803). Study participants remaining in the study will receive an appropriate rescue glucose-lowering regimen. [Table BDCM.4](#) provides details on the use of glucose-lowering medications for rescue and for treatment of acute conditions.

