#### **7.8.2.3. Management of Study Participants with Severe, Persistent Hyperglycemia during the Treatment Period**

An additional therapeutic intervention should be considered in study participants who develop severe, persistent hyperglycemia after randomization based on the following criteria (reference FDA Draft Guidance 2016):

- a) average FPG >270 mg/dL (>15.0 mmol/L) over any 2-week period or longer during the first 6 weeks postrandomization; or
- b) average FPG >240 mg/dL (>13.3 mmol/L) over any 2-week period or longer from Week 6 to Week 12 postrandomization; or
- c) average FPG >200 mg/dL (>11.1 mmol/L) over any 2-week period or longer from Week 12 to Week 18 postrandomization.

Investigators should first confirm that the study participant does not have an acute condition causing severe hyperglycemia and, after the first 12 weeks of the study, that the study participant is fully compliant with the assigned therapeutic regimen. The investigator will decide, in collaboration with the responsible clinical research physician (CRP) and in consultation with the study participant, on an appropriate glucose-lowering intervention (rescue intervention) after considering relevant clinical criteria. In general, insulin degludec will be the preferred rescue therapy for study participants assigned to LY3209590. See [Table BDCM.4](#) for allowed medications. Study participants who receive a new intervention for hyperglycemia management should also continue administering IP for the remaining period in the trial.

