4.8. Secondary and Additional Efficacy Analyses

The analysis population for the secondary analysis on HbA1c reduction is the EAS. Treatment comparison at 32 weeks will be used to assess the difference between the pooled LY arm and Degludec arm. The 2-sided 90% CI for the LS mean of the difference between pooled LY arm and Degludec arm in the change in HbA1c at 32 weeks will also be constructed.

A sensitivity analysis will be conducted to evaluate the “treatment policy” estimand, which is defined as the treatment differences in HbA1c at 32 weeks with the randomized treatment based

on all randomized patients who took at least one dose of study medication, and have baseline and at least one postbaseline measurement. In this analysis, all endpoint data regardless of treatment disposition status will be included and missing data will be imputed using multiple imputations to assess sensitivity to departures from the missing at random assumption. More specifically, the missing endpoint will be imputed multiple (for example, 100) times using the baseline data. Then, the inference based on the multiple imputations framework will be used (Rubin 1987).

The following secondary and additional efficacy analyses will be performed based on the EAS using the same MMRM model as the primary analysis with the addition term of HbA1c strata (<8.5% and \geq 8.5%) for non-HbA1c measures:

1. HbA1c change from baseline to Week 12;
2. Fasting blood glucose (FBG) by SMBG and change from baseline at Weeks 12 and 32;
3. Fasting serum glucose (FSG) by laboratory and change from baseline at Weeks 6, 12, 18, and 32;
4. Between-day glucose variability measured by the SD of the FBG (SMBG) at Week 12 and 32;
5. Six-point SMBG profile (pre-meal and 2-hour postprandial SMBG measurements for the morning, midday, and evening meals in 1 day) at Weeks 12 and 32. Since the baseline SMBG profile is not collected, the baseline FBG instead of baseline value of the dependent variable will be used as a covariate.
6. Within-day and between-day glucose variability measured by the standard deviation (SD) of 6-point SMBG. Since the baseline SMBG profile is not collected, the baseline SD of FBG instead of baseline value of the dependent variable will be adjusted as a covariate.

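### Protocol Section 8.2 orders study exit before any new glucose-lowering agent starts, contradicting the sections that keep participants in the study on rescue, acute insulin or therapy after stopping IP

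*Protocol*

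**What the plan says.** Protocol Section 8.2 lists circumstances in which participants will be discontinued from the study. One applies when a participant, whatever the reason, requires another agent of proven efficacy for the indication. In that case "discontinuation from the study occurs prior to introduction of the new agent". The item has no exception and no cross-reference.

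Other sections of the protocol give the opposite instruction for the same event:

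- **Rescue.** Section 5.1.1 (General considerations): "Study participants who need rescue therapy will continue on IP in the trial until they complete all study visits". Section 7.8.2.3: "Study participants who receive a new intervention for hyperglycemia management should also continue administering IP for the remaining period in the trial". That section names insulin degludec as the generally preferred rescue in the LY3209590 arms.
- **After stopping IP.** Section 5.1.1 (Study Period 3) encourages these participants to remain and adds: "Study participants remaining in the study will receive an appropriate rescue glucose-lowering regimen". Section 8.1.1 says they "may receive another glucose-lowering intervention, if appropriate, and will continue participating in the trial according to the protocol".
- **Acute or emergency therapy.** Section 7.8.2.4 allows non-study insulin for up to 2 weeks in total before Week 32. Beyond that, the investigator and the sponsor physician consult on whether the participant stays. Table BDCM.4 also allows insulin as acute therapy.
- **Safety follow-up.** Section 7.8.1 has participants return to their pre-study basal insulin after Visit 21, while they are still in the study.

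**The concern.** A site facing a participant who needs a new glucose-lowering drug has two instructions and no rule of precedence. Some sites could retain such participants while others withdraw them.

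If 8.2 were followed, three kinds of data would be lost:

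- **Week 32 HbA1c after rescue or after stopping IP.** The treatment-policy sensitivity analysis (SAP 4.8) is meant to use all endpoint data regardless of treatment disposition. For those who had left, "the missing endpoint will be imputed multiple (for example, 100) times using the baseline data", so a value the design intends to observe would be replaced by a model-based guess.
- **Hypoglycemia on IP after rescue.** SAP 4.10.3.2 uses all data up to study drug discontinuation for the treatment-period analyses. A rescued participant who should have stayed on IP would stop contributing time at risk. Hypoglycemia is a secondary safety objective.
- **Efficacy data after acute insulin.** The efficacy analysis set (EAS, SAP 4.1) drops data after rescue but expressly not after acute therapy. Withdrawing acute-insulin users would remove data that the primary analysis keeps.

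**Working it through.** **1. What triggers 8.2.** The rule acts on another agent and operates before a new agent is introduced. It therefore covers degludec rescue in an LY3209590 arm, prandial lispro as rescue, non-study insulin in an emergency, and a substitute regimen after IP is stopped. It does not cover a higher metformin dose (Table BDCM.4, note e) or a higher dose of another allowed oral drug (Section 7.7.2), because no new agent is introduced.

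**2. The instructions side by side.**

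| Event | Section 8.2 | Other sections |
|---|---|---|
| New rescue agent | Leave the study first | Continue IP and all visits (5.1.1, 7.8.2.3) |
| New agent after IP is stopped | Leave the study first | May be treated and stay (5.1.1, 8.1.1) |
| Non-study insulin, up to 2 weeks | Leave the study first | Allowed on study (7.8.2.4, Table BDCM.4) |
| Non-study insulin, over 2 weeks | Leave the study first | Decide by consultation (7.8.2.4) |
| Basal insulin resumed in follow-up, where it differs from study treatment | Leave the study first | Planned for completers (7.8.1) |

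The last row shows that 8.2 cannot be applied literally even to participants who complete treatment as planned.

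**3. Effect on each analysis set.** For rescued and off-IP participants the EAS already excludes later data, so 8.2 takes nothing more from the primary analysis. The loss falls on the treatment-policy analysis and, for rescued participants still on IP, on hypoglycemia. Only acute-insulin users would lose data from the primary analysis.

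**4. Counts and weeks.** Each 1% of the 375 randomized who start a new agent is 0.01 × 375 = 3.75, about 4 participants. For threshold-based rescue, Section 7.8.2.3 needs a 2-week glucose average, so the earliest start is about Week 2, and its last stated window ends at Week 18. The treatment time lost per participant would be:

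- start at Week 2: 32 − 2 = 30 weeks, 30/32 = 94%
- start at Week 18: 32 − 18 = 14 weeks, 14/32 = 44%

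This range does not apply to acute insulin or off-IP therapy, which can start at any time.

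**5. Power of the primary comparison.** Inputs from Protocol Section 10.1: 300 completers (200 pooled LY3209590, 100 degludec), margin 0.4, SD 1.1, true difference 0, two-sided alpha 0.1. With the normal approximation, SE = 1.1 × √(1/n₁ + 1/n₂) and power = Φ(0.4/SE − 1.645).

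- Planned, 200 vs 100: SE = 0.1347, power = 0.907. This reproduces the stated 90%.
- 1% lost, 198 vs 99: SE = 0.1354, power = 0.905.
- 5% lost, 190 vs 95: SE = 0.1382, power = 0.894.

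The 1% to 5% is an assumed share of completers leaving because of acute insulin, beyond the planned 20% dropout. The repeated-measures model would recover part of the loss from earlier visits.

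**6. Sulfonylureas.** Section 7.7.1 includes them among the allowed rescue agents. Table BDCM.4 marks them N for rescue. This is a separate, smaller mismatch.

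**The case against.** The best defense is that the intent is plain and sites would follow it. The 8.2 item is one general line under investigator decision. Against it stand several specific, mutually consistent sections and a rescue column in Table BDCM.4. A sponsor physician also takes part, since rescue is decided "in collaboration with the responsible clinical research physician (CRP) and in consultation with the study participant". Section 7.7.1 even names the expected exceptions (rescue therapy and short-term emergency insulin) in its own rule on new glucose-lowering drugs. Section 8.2 still asks for adverse event and safety follow-up after exit.

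Most of this stands, and it makes widespread withdrawal unlikely. It does not remove the contradiction. The 8.2 wording is mandatory, and investigator discretion already has its own sub-item. The exceptions in 7.7.1 attach to a different consequence (stop the drug and file a deviation), so they do not modify 8.2.

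Three stronger readings are tempting, and the documents do not support them:

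- A reader might infer that 8.2 removes everyone whose glucose-lowering treatment is intensified. It does not reach dose increases of existing drugs.
- A reader might infer that the primary analysis is compromised. For rescue and IP discontinuation the EAS excludes the later data by design, and the acute-insulin effect is small under the assumed rates.
- A reader might infer that the SAP leaves rescue undefined. Protocol Sections 5.1.1 and 7.8.2.3 already identify rescue as a new intervention for severe, persistent hyperglycemia, and the SAP separates it from acute therapy. No added definition is needed.

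**Conclusion.** The concern holds as a wrong stated rule in Section 8.2, limited to cases where a new agent is introduced. The retention design is clear elsewhere and needs no change.

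The size of the harm is unknown. The documents give no rate of rescue, acute insulin or post-IP therapy, and it is not known which instruction sites would follow. If 8.2 were followed, the loss would fall mainly on a sensitivity analysis and on hypoglycemia data after rescue. The effect on primary power is likely small: 90.7% to between 90.5% and 89.4% under the assumed 1% to 5% loss. The correction is worth making because the contradiction is certain and the remedy is cheap.

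**What to change.** Delete the 8.2 sub-bullet, or state that it does not apply to:

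1. rescue therapy under 7.7.1, 7.8.2.3 and Table BDCM.4;
2. acute or emergency therapy under 7.8.2.4, including use beyond 2 weeks when retention is agreed with the sponsor physician (a flat 14-day cap would leave that group in conflict);
3. glucose-lowering therapy after IP is stopped, under 5.1.1 and 8.1.1;
4. basal insulin resumed in safety follow-up under 7.8.1.

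If the sub-bullet is kept, add that agents the protocol does not permit are handled under 7.7.1 (stop the drug and file a deviation), without automatic study exit.

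Separately, make 7.7.1 and Table BDCM.4 agree on whether a sulfonylurea may be used as rescue.

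The cost is a short wording change in 8.2 and one correction for sulfonylureas. No visits, procedures or participants are added, and the SAP needs no change.

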### **8.3. Lost to Follow-Up**

A study participant will be considered lost to follow-up if he or she repeatedly fails to return for scheduled visits and is unable to be contacted by the study site. Site personnel are expected to make diligent attempts to contact study participants who fail to return for a scheduled visit or were otherwise unable to be followed up by the site.

## 9. Study Assessments and Procedures

Section 2 lists the Schedule of Activities, with the study procedures and their timing (including tolerance limits for timing).

Appendix 2 lists the laboratory tests that will be performed for this study.

Unless otherwise stated in the subsections below, all samples collected for specified laboratory tests will be destroyed within 60 days of receipt of confirmed test results. Certain samples may be retained for a longer period, if necessary, to comply with applicable laws, regulations, or laboratory certification standards.

